5.4.1 Indicate the elements of informed consent to be omitted or altered

NA

5.4.2 Indicate why the research could not practicably be carried out without the omission or alteration of consent elements

NA

5.4.3 Describe why the research involves no more than minimal risk to subjects.

NA

5.4.4 Describe why the alteration/omission will not adversely affect the rights and welfare of subjects.

NA

5.4.5 If the research involves using identifiable private information or identifiable biospecimens, describe why the research could not be practicably be carried out without using such information or biospecimens in an identifiable format.

NA

5.4.6 Debriefing

Explain whether and how subjects will be debriefed after participation in the study. If subjects will not be debriefed, provide a justification for not doing so. Add any debriefing materials to the study in CATS IRB.

NA

5.5 Informed consent will not be obtained – request to completely waive the informed consent requirement

Review “HRP-410-Checklist -Waiver or Alteration of Consent Process” to ensure that you have provided sufficient information.

5.5.1 Indicate why the research could not practicably be carried out without the waiver of consent

NA

5.5.2 Describe why the research involves no more than minimal risk to subjects.

NA

5.5.3 Describe why the alteration/omission will not adversely affect the rights and welfare of subjects.

NA

5.5.4 If the research involves using identifiable private information or identifiable biospecimens, describe why the research could not be practicably be carried out without using such information or biospecimens in an identifiable format.

NA

5.5.5 Additional pertinent information after participation

Explain if subjects will be provided with additional pertinent information after participation. If not applicable, indicate "not applicable."

NA

5.6 Consent – Other Considerations

5.6.1 Non-English-Speaking Subjects

Indicate what language(s) other than English are understood by prospective subjects or representatives.

If subjects who do not speak English will be enrolled, describe the process to ensure that the oral and written information provided to those subjects will be in that language. Indicate the language that will be used by those obtaining consent.

Indicate whether the consent process will be documented in writing with the long form of the consent documentation or with the short form of the consent documentation. Review "HRP-091 –SOP- Written Documentation of Consent" and "HRP-103 -Investigator Manual" to ensure that you have provided sufficient information.

NA

5.6.2 Cognitively Impaired Adults

Refer "HRP-417 -CHECKLIST- Cognitively Impaired Adults" for information about research involving cognitively impaired adults as subjects.

5.6.2.1 Capability of Providing Consent

Describe the process to determine whether an individual is capable of consent.

NA

5.6.2.2 Adults Unable to Consent

Describe whether and how informed consent will be obtained from the legally authorized representative. Describe who will be allowed to provide informed consent. Describe the process used to determine these individual's authority to consent to research.

For research conducted in the state of Pennsylvania, review "HRP-013 -SOP- Legally Authorized Representatives, Children and Guardians" to be aware of which individuals in the state of Pennsylvania meet the definition of "legally authorized representative."

For research conducted outside of the state of Pennsylvania, provide information that describes which individuals are authorized under applicable law to consent on behalf of a prospective subject to their participation in the procedure(s) involved in this research. One method of obtaining this information is to have a legal counsel or authority review your protocol along with the definition of "children" in "HRP-013 -SOP- Legally Authorized Representatives, Children, and Guardians."

NA

5.6.2.3 Assent of Adults Unable to Consent

Describe the process for assent of the subjects. Indicate whether assent will be required of all, some or none of the subjects. If some, indicate which subjects will be required to assent and which will not.

If assent will not be obtained from some or all subjects, provide an explanation of why not.

Describe whether assent of the subjects will be documented and the process to document assent. The IRB allows the person obtaining assent to document assent on the consent document and does not routinely require assent documents and does not routinely require subjects to sign assent documents.

NA

1. Subjects who are not yet adults (infants, children, teenagers)

5.6.3.1 Parental Permission

Describe whether and how parental permission will be obtained. If permission will be obtained from individuals other than parents, describe who will be allowed to provide permission. Describe the process used to determine these individual's authority to consent to each child's general medical care.

For research conducted in the state of Pennsylvania, review "HRP-013-SOP- Legally Authorized Representatives, Children and Guardians" to be aware of which individuals in the state of Pennsylvania meet the definition of "children."

For research conducted outside of the state of Pennsylvania, provide information that describes which persons have not attained the legal age for consent to treatments or procedures involved in the research, under the applicable law of the jurisdiction in which research will be conducted. One method of obtaining this information is to have a legal counsel or authority review your protocol along with the definition of "children" in "HRP-013-SOP- Legally Authorized Representatives, Children, and Guardians."

NA

5.6.3.2 Assent of subjects who are not yet adults

Indicate whether assent will be obtained from all, some, or none of the children. If assent will be obtained from some children, indicate which children will be required to assent. When assent of children is obtained describe whether and how it will be documented.

NA.

6.0 HIPAA Research Authorization and/or Waiver or Alteration of Authorization

This section is about the access, use or disclosure of Protected Health Information (PHI). PHI is individually identifiable health information (i.e., health information containing one or more 18 identifiers) that is transmitted or maintained in any form or medium by a Covered Entity or its Business Associate. A Covered Entity is a health plan, a health care clearinghouse or health care provider who transmits health information in electronic form. See "HRP-103 -Investigator Manual" for a list of the 18 identifiers.

If requesting a waiver/alteration of HIPAA authorization, complete sections 6.2 and 6.3 in addition to section 6.1. The Privacy Rule permits waivers (or alterations) of authorization if the research meets certain conditions. Include only information that will be accessed with the waiver/alteration.

[Do not type here]

6.1 Authorization and/or Waiver or Alteration of Authorization for the Uses and Disclosures of PHI

Check all that apply:

- Not applicable, no identifiable protected health information (PHI) is accessed, used or disclosed in this study. *[Mark all parts of sections 6.2 and 6.3 as not applicable]*
- Authorization will be obtained and documented as part of the consent process. *[If this is the only box checked, mark sections 6.2 and 6.3 as not applicable]*
- Partial waiver is requested for recruitment purposes only (Check this box if patients' medical records will be accessed to determine eligibility before consent/authorization has been obtained). *[Complete all parts of sections 6.2 and 6.3]*
- Full waiver is requested for entire research study (e.g., medical record review studies). *[Complete all parts of sections 6.2 and 6.3]*
- Alteration is requested to waive requirement for written documentation of authorization (verbal authorization will be obtained). *[Complete all parts of sections 6.2 and 6.3]*

6.2.Waiver or Alteration of Authorization for the Uses and Disclosures of PHI

6.2.1Access, use or disclosure of PHI representing no more than a minimal risk to the privacy of the individual

6.2.1.1 Plan to protect PHI from improper use or disclosure

Include the following statement as written – DO NOT ALTER OR DELETE unless this section is not applicable because the research does not involve a waiver of authorization. **If the section is not applicable, remove the statement and indicate as not applicable.**

Information is included in the “Confidentiality, Privacy and Data Management” section of this protocol.

6.2.1.2 Plan to destroy identifiers or a justification for retaining identifiers

Describe the plan to destroy the identifiers at the earliest opportunity consistent with the conduct of the research. Include when and how identifiers will be destroyed. If identifiers will be retained, provide the legal, health or research justification for retaining the identifiers.

All study materials that have identifiable information will be kept until notified by the sponsor. If the subject doesn't qualify from a phone call, the screening form will be placed in the shredder due to PHI.

6.2.2Explanation for why the research could not practically be conducted without access to and use of PHI

Provide an explanation for why the research could not practically be conducted without access to and use of PHI.

Research team has access to participant's medical record after the ICF is signed. Research needs to use PHI to ensure subject meets eligibility criteria.

6.2.3 Explanation for why the research could not practically be conducted without the waiver or alteration of authorization

Provide an explanation for why the research could not practically be conducted without the waiver or alteration of authorization.

Participants are screened prior to performing ICF process to help determine if the patient is potentially eligible for the study. This helps sift through candidates for appointments so patient's time is not wasted.

6.3 Waiver or alteration of authorization statements of agreement

By submitting this study for review with a waiver of authorization, you agree to the following statement – DO NOT ALTER OR DELETE unless this section is not applicable because the research does not involve a waiver or alteration of authorization. **If the section is not applicable, remove the statement and indicate as not applicable.**

Protected health information obtained as part of this research will not be reused or disclosed to any other person or entity, except as required by law, for authorized oversight of the research study, or for other permitted uses and disclosures according to federal regulations.

The research team will collect only information essential to the study and in accord with the 'Minimum Necessary' standard (information reasonably necessary to accomplish the objectives of the research) per federal regulations.

Access to the information will be limited, to the greatest extent possible, within the research team. All disclosures or releases of identifiable information granted under this waiver will be accounted for and documented.

7.0 Study Design and Procedures

Data collection materials that will be seen or used by subjects in your study must be uploaded to CATS IRB (<http://irb.psu.edu>). **DO NOT** include any actual data collection materials in this protocol (e.g., actual survey or interview questions)

7.1 Study Design

Describe and explain the study design.

This is a prospective, single-center, patient and assessor-blinded, double-arm clinical study. Subjects will be enrolled at the Penn State Eye Center. Eligible subjects must be anticipated to undergo bilateral sequential cataract surgery. Both eyes from each patient will be considered study eyes.

Candidate patients who give written consent to participate in the study will be enrolled and screened to determine study eligibility, then examined to obtain their medical and ophthalmic history and establish their baseline ocular condition. Qualified subjects will be randomized to receive one of two study devices in both eyes. Post-operatively, subjects will undergo examination at 4 protocol-specific visits at regularly scheduled intervals through 3 months post-operatively, as shown in **APPENDIX 1: SCHEDULE OF CLINICAL ASSESSMENTS/PROCEDURES**.

7.2 Study Procedures

Provide a step by step description of all research procedures being conducted (broken down by visit, if applicable) including such information as below (where and when applicable); describe the following:

- **HOW:** (e.g., data collection via interviews, focus groups, forms such as surveys and questionnaires, medical/school records, audio/video/digital recordings, photographs, EKG procedures, MRI, mobile devices such as electronic tablets/cell phones, observations, collection of specimens, experimental drug/device testing, manipulation of behavior/use of deception, computer games, etc.)
- **WHERE:** (e.g., classrooms, labs, internet/online, places of business, medical settings, public spaces, etc.)

All potential participants will complete all of the pre-operative assessments as part of Standard of Care treatment. At that time, the Principle Investigator will introduce the study to the potential participants and go over each lens that could be implanted. If patient agrees to move forward with study participation, the coordinator will complete screening and perform the consent process. The study participants will be provided two questionnaires to complete that ask about how much difficulty they presently have seeing things at distance, intermediate and near. It will also assess which specific visual disturbances (eg blurry vision, glare) they are experiencing before surgery takes place.

Randomization, the IOL randomization code list will be provided by the Dept. of Public Health Sciences. This determines which IOL would be implanted for each patient and will be assigned once the consent is

signed and it is determined that the subject has met all eligibility criteria. The PI will be unblinded to the lens that will be implanted as he will be doing the surgical procedure.

Post-operative assessments that occur for eye #1- Day 1 and week 1 as well as eye #2- Day 1 will be performed by [name] as part of standard of care. During this time, if an AE or SAE is identified, it would be reviewed and causality/IOL relationship will be determined by another Ophthalmologist, [name] who will be unblinded. At the 1 month and 3 month follow-up visits, assessments would be performed by the Blinded investigator, [name]. At study completion, after all study procedures are completed the coordinator will then pull the subject envelope containing the wallet card that reveals which IOL lens was implanted in both the right and left eye.

Table 1: Schedule of Clinical Assessments / Procedures

Assessment / Procedure	Protocol Visit							
	Pre-operative/ Visit 1	Operative #1/ Visit 2	1 Day #1/ Visit 3	1 Week / Visit 4	Operative #2/ Visit 5	1 Day #2/ Visit 6	1 Month/ Visit 7	3 Month/ Visit 8
Medical and ophthalmic history	SOC							
Slit lamp examination	SOC		SOC	SOC		SOC	SOC	SOC
Dilated fundus examination	SOC						SOC	
Intraocular pressure	SOC		SOC	SOC		SOC	SOC	SOC
Pre-operative biometry	SOC							
Macular optical-coherence tomography	SOC							
Corneal topography	SOC							
Informed consent	R							
Randomization to study arm	R							
Cataract extraction with IOL implantation		SOC			SOC			
Manifest refraction				SOC			SOC	SOC
Snellen uncorrected distance acuity	SOC		SOC	SOC		SOC	SOC	SOC
Uncorrected distance visual acuity (UDVA) monocular and binocular							R	R
Corrected distance visual acuity (CDVA) monocular and binocular							R	R
Uncorrected intermediate visual acuity (UIVA) monocular							R	R

and binocular								
Distance corrected intermediate visual acuity (DCIVA) monocular and binocular						R	R	
Uncorrected near visual acuity (UNVA) monocular and binocular						R	R	
Distance corrected near visual acuity (DCNVA) monocular and binocular						R	R	
Defocus Curve Testing (binocular only)								R
Un-blinding								R
Patient Reported Outcomes	R							R
Adverse Event Monitoring	R	R	R	R	R	R	R	R
Urine Pregnancy test	R							

SOC = standard-of-care; R = research

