9.1 Periodic evaluation of data

Describe the plan to periodically evaluate the data collected regarding both harms and benefits to determine whether subjects remain safe.

Outcome measures will be reviewed after 10, and again after 20 subjects have completed all study related assessments.

Adverse events and SAEs will be monitored continuously by the blinded examiner. The expected or unexpected adverse events will not unblind the examiner because everyone receives an IOL. The examiner would not be able to decipher which lens could be related to an event.

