9.2 Data that are reviewed

Describe the data that are reviewed, including safety data, untoward events, and efficacy data.

Refractive outcomes and mean best-corrected distance visual acuity will be reviewed to ensure mean prediction errors (MPEs) and logMAR visual acuities are in line with what is reported in the peer-reviewed literature and FDA Summary of Safety and Effectiveness for the Alcon Vivity IOL.

AEs and SAE's will be reviewed on a case-by-case basis by the blinded examiner.

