10.0 Risks

List the reasonably foreseeable risks, discomforts, hazards, or inconveniences to the subjects related to the subjects' participation in the research. Include as may be useful for the IRB's consideration, a description of the probability, magnitude, duration and reversibility of the risks. Consider all types of risk including physical, psychological, social, legal, and economic risks. Note: Loss of confidentiality is a potential risk when conducting human subject research.

- If applicable, indicate which procedures may have risks to the subjects that are currently unforeseeable.
- If applicable, indicate which procedures may have risks to an embryo or fetus should the subject be or become pregnant.

- If applicable, describe risks to others who are not subjects.

The risks to study subjects are the same risks as those patients would normally incur before, during, and after cataract surgery.

Intraocular lenses that seek to provide intermediate or near vision without glasses may be associated with additional risks that include blurry vision not correctable with glasses or contact lenses and subjective visual disturbances including starbursts, haloes, glare, hazy or blurry vision. In an FDA trial that compared similar lenses to the ones being evaluated in this study, these visual phenomena were severe or very bothersome in 3-4% of patients. This specific risk has been explained in detail in the informed consent form, and will also be reviewed verbally at the time of consent for surgery.

There is a small risk to the subjects of loss of confidentiality. Safeguards as described in the Data Management Plan are in place to minimize these risk.

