18.0 Adverse Event Reporting

18.1 Reporting Adverse Reactions and Unanticipated Problems to the Responsible IRB

By submitting this study for review, you agree to the following statement – DO NOT ALTER OR DELETE:

In accordance with applicable policies of The Pennsylvania State University Institutional Review Board (IRB), the investigator will report, to the IRB, any observed or reported harm (adverse event) experienced by a subject or other individual, which in the opinion of the investigator is determined to be (1)

unexpected; and (2) probably related to the research procedures. Harms (adverse events) will be submitted to the IRB in accordance with the IRB policies and procedures.

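### Early adverse events have two reviewers of opposite blinding status, and lens-relatedness is rated either with the lens known (early visits) or by nobody named (1 and 3 months)

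*Combined protocol and SAP*

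**What the plan says.** Section 7.2 (Study Procedures) describes the standard-of-care checks at eye 1 Day 1, eye 1 Week 1 and eye 2 Day 1, and then sets a rule for events found in that window: "During this time, if an AE or SAE is identified", "it would be reviewed and causality/IOL relationship will be determined by another Ophthalmologist", "who will be unblinded". The same paragraph turns to the later visits: "At the 1 month and 3 month follow-up visits, assessments would be performed by the Blinded investigator".

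Section 9.1 says "Adverse events and SAEs will be monitored continuously by the blinded examiner". It adds that events cannot reveal the allocation because both groups get an intraocular lens, and that the examiner could not work out which lens an event might relate to. Section 9.2 says "AEs and SAE's will be reviewed on a case-by-case basis by the blinded examiner". Neither section mentions the ophthalmologist of 7.2 or limits the examiner's role to particular visits.

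Table 1 schedules adverse event monitoring at all eight visits. Section 7.1 declares patients and assessors blinded.

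**The concern.** Whether an event is attributed to the lens is a matter of judgement. A rater who knows the lens can, without intending to, apply a different threshold to a lens with a special optical design than to a monofocal one. If some visits are rated that way and others have no assigned rater, attributions are not comparable across visits and may differ between arms for reasons unrelated to the lenses.

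The second matter is the assessor's blind. The blinded examiner of 9.1 and 9.2 is probably the person who measures the primary endpoint, binocular distance-corrected intermediate acuity at 3 months. That person is not assigned the early visits, so reviewing early events would have to rely on records or on colleagues, some of whom know the lens.

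**Working it through.** No arithmetic applies, because the point rests on no sample size, power or event rate. The check is to set the sections side by side, by visit.

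| Visits in Table 1 | Reviewer under 7.2 | Reviewer under 9.1 and 9.2 | Assigned to rate IOL relationship |
|---|---|---|---|
| 3, 4, 6 (eye 1 Day 1, Week 1; eye 2 Day 1) | Another ophthalmologist, unblinded | Blinded examiner | The 7.2 ophthalmologist, knowing the lens |
| 7, 8 (1 and 3 months) | None named | Blinded examiner | Nobody |
| 2, 5 (operative days) | Not expressly named | Blinded examiner | Not expressly named |

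Visit 1 precedes implantation, so lens relationship does not arise there.

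1. **Who reviews.** At Visits 3, 4 and 6, which are three of the five post-operative follow-up visits, 7.2 names an unblinded reviewer and section 9 names a blinded one. Neither text acknowledges the other. This is the direct conflict.

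2. **Who rates relatedness.** Only 7.2 assigns this. Sections 9.1 and 9.2 give the blinded examiner monitoring and review, not the causality decision, and the 9.1 remark that the examiner could not link an event to a lens points away from that examiner as the rater. The two texts do not compete over this decision. It is made unblinded at the early visits and left unassigned at Visits 7 and 8, although Table 1 schedules monitoring there.

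3. **Whether the acuity blind is exposed.** Three links are needed. First, the blinded examiner of section 9 must be the blinded investigator of 7.2. This is likely, since no other blinded examiner is described, but names are removed. Second, that person must see early-event files or discuss them with unblinded staff. Sections 9.1 and 9.2 read literally imply review of those events, and no masking is described. Third, the material or the contact must reveal the lens. This is an assumption, because the documents do not say what event records contain. The 9.1 reassurance does not close the third link: that every patient has a lens shows that having one is uninformative, but says nothing about records or conversations that identify which one.

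**The case against.** The strongest reply is that one person can monitor events while another attributes them, so the sections can be read together, and that a device-relationship decision may need the device identity. Using an ophthalmologist other than the operating investigator is already a safeguard. The wallet card naming the lens stays in an envelope until all study procedures are finished. The data plan is in a separate form, which may deal with access to records.

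Much of this stands. A reader might infer that 7.2 and section 9 cannot both be followed on causality; they can, because section 9 never assigns that decision. What remains is the double assignment of review at the early visits and the missing rater later. The need for device identity also does not stop a first rating being recorded without it.

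Three stronger readings are tempting and should not be drawn.

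- **Visual complaints as a clue to the arm.** Section 10 says "Intraocular lenses that seek to provide intermediate or near vision without glasses may be associated with additional risks". But section 2.2 reports similar disturbance rates for Vivity and a monofocal lens considered similar to enVista, and section 2.1 describes Vivity's glare and halo profile as approaching a monofocal's. The documents do not support such complaints as a marker of allocation.
- **A size taken from the 3-4% in section 10.** That figure is for severe or very bothersome phenomena in an earlier trial of similar lenses. It is not tied to Day 1 or Week 1, the visits the 7.2 rule covers, so it does not measure this problem.
- **A direct effect on IRB reporting.** Section 18.1 turns on events that are unexpected and "probably related to the research procedures", in the investigator's opinion. That is a different judgement from relationship to the lens.

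It is also fair that the blinded investigator performs the assessments at Visits 7 and 8 and will find some events whoever collects reports. The fix has to allow for this.

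**Conclusion.** The concern holds as a minor point. Review roles conflict for events found at Visits 3, 4 and 6. The only assigned lens-relatedness rating is made knowing the lens, and none is assigned at Visits 7 and 8. This can bias how events are attributed between the two lenses.

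The size is limited. Relatedness is not among the endpoints in sections 1.2 and 1.3, and the tests in section 9.7 cover only acuity and refractive outcomes, so no planned comparison depends on it. No sample size or power figure changes.

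A reader might go further and infer that the 3-month acuity endpoint is biased. The documents do not show that. Exposure of the acuity examiner is a possible route that rests on two assumptions: that the blinded examiner of section 9 is the acuity assessor, and that event files or contact with unblinded staff would reveal the lens. The 9.1 assurance does not rule the route out, which is reason enough to close it by wording.

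**What to change.** Reconcile 7.2 with 9.1 and 9.2 into one event-review pathway for all visits:

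- The ophthalmologist already named in 7.2 reviews every AE and SAE, at every visit, and records the IOL-relationship rating from a summary that omits lens identity. Allocation is disclosed to that reviewer only after the rating is recorded. This requires that the reviewer has no other access to the allocation before rating.
- The blinded examiner does not review early-event files. At Visits 7 and 8 that examiner completes acuity testing, and at Visit 8 defocus testing, before asking about adverse events, and passes any event found to the reviewer.
- Sections 9.1 and 9.2 are amended to match. The 9.1 statement that events cannot unblind is replaced by a description of this safeguard.
- The blinding status of each reviewer is stated, including the co-investigator who does the periodic review in section 9.5.

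The pathway concerns rating and review only and changes no treatment, visit or endpoint. It needs protocol wording and no extra staff. The downside is that someone outside the blinded assessment must prepare an event summary with lens identity left out for the first rating.
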